7.3.2. Percentage of recognized words

• Computation of the Endpoint

The percentage of recognized words will be computed by visit as the number of recognized words divided by 50 and multiplied by 100, separately for each ear. Missing data will not be imputed.

• Analysis of the Endpoint

The percentage of recognized words will be summarized descriptively for treated and untreated ears separately by visit and treatment group for subjects in the FAS.

7.3.3. Change from baseline in percentage of recognized words

• Computation of the Endpoint

The change from baseline to each post-baseline visit in percentage of recognized words will be computed as $100^{(w/50)} - (b/50)$ where "w" is the frequency of words recognized at the post-baseline visit and "b" is the frequency of words recognized at baseline.

• Analysis of the Endpoint

The change from baseline in percentage of recognized words will be summarized descriptively for treated and untreated ears separately by visit and treatment group for subjects in the FAS.

A Line graph (with standard error bars) will be created for the observed mean change from baseline in percentage of recognized words for treated ears by post-baseline visit and treatment group for subjects in the FAS. Post-baseline visit will be plotted on the x-axis and the observed mean change from baseline in percentage of recognized words for treated ears will be plotted on the y-axis. Each treatment group will be presented as a separate line in the plot.

- 7.3.4. Improvement \geq 10% (5 words) from baseline in percentage of recognized words
 - Computation of the Endpoint

Improvement $\geq 10\%$ in percentage of recognized words at each post-baseline visit for treated ears will be computed as 1 if the change from baseline in percentage of recognized words $\geq 10\%$ and as 0, otherwise where change from baseline is non-missing. Missing data will not be imputed.

• Analysis of the Endpoint

The incidence of improvement ≥10% in percentage of recognized words at each postbaseline visit for treated ears will be summarized using frequencies and percentages by visit and treatment group for subjects in the FAS.

In treated ears only for subjects in the FAS, the GEE model described in Section 7.3.1 will be repeated for improvement \geq 10% in percentage of recognized words.

7.3.5. Change from Baseline in Arcsine-transformed WR

• Computation of the Endpoint

The arcsine-transformed WR (Studebaker, 1985) will be computed by visit for treated ears as

$$R = \arcsin\sqrt{w/(n+1)} + \arcsin\sqrt{(w+1)/(n+1)}$$

where "R" is the transformed radians, "w" is the frequency of words recognized, and "n" is the number of words in the word test (n = 50 for WR assessments). Missing data will not be imputed.

Change from baseline to each post-baseline visit in arcsine-transformed WR will be computed as R post-baseline – R at baseline.

• Analysis of the Endpoint

In treated ears only for subjects in the FAS, post-baseline treatment group comparisons through day 90 will be performed using a MMRM model for change from baseline in arcsine-transformed WR with fixed covariates for treatment group, visit, interaction between visit and treatment group, baseline WR score, the interaction between baseline WR score and visit, and randomization stratification factors. If the model fails to converge, the randomization stratification factors will be removed from the model. An unstructured covariance will be used to model the within-subject errors. Linear contrasts will be constructed to estimate the treatment effect for the mean change from baseline in arcsine-transformed WR by visit (e.g., estimated Least squares (LS) Mean differences by visit).

A Line graph (with standard error bars) will be created for the adjusted (least squares) mean change from baseline in arcsine-transformed WR for treated ears by post-baseline visits through day 90 and treatment group for subjects in the FAS. Post-baseline visit will be plotted on the x-axis and the adjusted (least squares) mean change from baseline in arcsine-transformed WR for treated ears will be plotted on the y-axis. Each treatment group will be presented as a separate line in the plot.

7.3.6. Improvement from baseline above Thornton-Raffin upper confidence limits

• Computation of the Endpoint

Improvement is defined as an increase in post-baseline WR score above the Thornton-Raffin (1978) 95% upper limit (Section 14.1) based on baseline (average of Lead-In and End of Lead-In/Treatment scores) assessment. Subjects with improvement will be computed as 1, and as 0, otherwise for each visit and by ear (left, right). Missing data will not be imputed. Left and right ears will be mapped to treated and untreated for analysis. The incidence of WR improvement will be computed as proportion of subjects who have a WR in Quiet improvement based on the Thornton-Raffin confidence limits.

The Thornton-Raffin 95% confidence intervals reported in Section 14.1 will be used directly and not computed.

• Analysis of the Endpoint

The incidence of WR improvement will be summarized descriptively for treated and untreated ears separately by visit and treatment group for subjects in the FAS.

Scatter plots displaying the percentage of recognized words (Section 7.3.2) at baseline versus those at post-baseline, along with the Thornton-Raffin confidence intervals, will be generated for each visit separately for treated and untreated ears.

7.4. Words-In-Noise

The WIN test, using the NU-6 list, was developed as an instrument to quantify the ability of listeners to understand monosyllabic words in background noise using multitalker babble (Wilson, 2003). Materials are recorded at 7 signal-to-noise ratios (0, 4, 8, 12, 16, 20, 24 dB) that are presented in a descending manner. This test is conducted by presenting 2 lists of 35 recorded words (70 total) to each ear. The number of and percentage of correctly recognized words at each signal-to-noise ratio will be recorded separately by ear. The overall WIN score will be recorded as the percentage of correctly recognized words across all signal-to-noise ratios by visit and ear. If all 70 words are not assessed in each ear, the WIN test score will not be calculated. This test will occur at the Screening/Start of Lead-In, Lead-In, End of Lead-In/Treatment, Day 30, Day 60, Day 90, Day 180, and Day 270 visits. Testing will be performed at 80 dB sound pressure level (SPL). Word lists will be rotated at each visit.

WIN results will be presented in a data listing for the FAS.

7.4.1. Percentage of recognized words

• Computation of the Endpoint

At each visit and by ear (left, right), the number of words classified as correctly recognized at each signal-to-noise ratio will be recorded. The overall WIN score will also be computed as the number of words correctly recognized across all signal-to-noise ratios. Left and right ears will be mapped to treated and untreated for analysis. The percentage of recognized words will be computed for each signal-to-noise ratio by visit as the number of recognized words divided by 10 and multiplied by 100, separately for each ear. The percentage of recognized words overall by visit will be computed as the number of recognized words divided by 70 and multiplied by 100, separately for each ear.

- Analysis of the Endpoint
- 7.4.2. The percentage of recognized words at each signal-to-noise ratio and overall will be summarized descriptively for treated and untreated ears separately by visit

Version Date: 2023-01-19

and treatment group for subjects in the FAS.Change from baseline in percentage of recognized words

• Computation of the Endpoint

The change from baseline to each post-baseline visit in percentage of recognized words at each signal-to-noise ratio will be computed as $100^*[(w/10) - (b/10)]$ where "w" is the frequency of words recognized at the post-baseline visit and "b" is the frequency of words recognized at baseline. The change from baseline to each post-baseline visit in percentage of recognized words overall will be computed using the same algorithm, but with 70 words in the denominator instead of 10. Missing data will not be imputed.

• Analysis of the Endpoint

The change from baseline in percentage of recognized words at each signal-to-noise ratio and overall will be summarized descriptively for treated and untreated ears separately by visit and treatment group for subjects in the FAS.

The primary analysis for the key secondary endpoint, WIN improvement based on mean change from baseline in percentage of recognized words overall at Day 90, will be based on the following MMRM model. In treated ears only for subjects in the FAS, post-baseline treatment group comparisons through day 90 will be performed using a MMRM model for change from baseline in percentage of recognized words overall with fixed covariates for treatment group, visit, interaction between visit and treatment group, baseline WIN score overall, the interaction between baseline WIN score overall and visit, and randomization stratification factors. If the model fails to converge, the randomization stratification factors will be removed from the model. An unstructured covariance will be used to model the within-subject errors. Linear contrasts will be constructed to estimate the treatment effect for the mean change from baseline in percentage of recognized words overall by visit (e.g., estimated Least squares (LS) Mean differences by visit).

Line graphs (with standard error bars) will be created for the adjusted (least squares) mean change from baseline in percentage of recognized words overall estimates for treated ears by post-baseline visit and treatment group for subjects in the FAS. Post-baseline visit will be plotted on the x-axis and the adjusted (least squares) mean change from baseline in percentage of recognized words overall estimates for treated ears will be plotted on the yaxis. Each treatment group will be presented as a separate line in the plot.

• Sensitivity Analyses of the Endpoint

The MMRM will be repeated using treated ears for subjects in the PPAS.

7.4.3. Improvement ≥10% (7 words) from baseline in percentage of recognized words overall

• Computation of the Endpoint

Improvement $\geq 10\%$ from baseline in percentage of recognized words overall at each postbaseline visit for treated ears will be computed as 1 if the change from baseline in percentage of recognized words overall $\geq 10\%$ and as 0, otherwise where the change is not missing. Missing data will not be imputed. Improvement $\geq 10\%$ (7 words) from baseline in percentage of recognized words will not be computed for each signal-to-noise ratio.

• Analysis of the Endpoint

The incidence of improvement ≥10% from baseline in percentage of recognized words overall at each post-baseline visit for treated ears will be summarized using frequencies and percentages by visit and treatment group for subjects in the FAS.

In treated ears only for subjects in the FAS, post-baseline treatment group comparisons for incidence of improvement ≥10% from baseline in percentage of recognized words overall will be analyzed using a GEE model. With the binomial distribution assumption and logit link, the model will include fixed effects of treatment group, visit, interaction between visit and treatment group, baseline WIN score, interaction between baseline WIN score and visit, and randomization stratification factors. If the model fails to converge, the randomization stratification factors will be excluded from the model. The odds ratios along with 95% CIs and p-values between treatment groups will be reported by visit.

- 7.4.4. Spearman-Kärber estimates of dB thresholds for word recognition (25th, 50th (median) and 75th percentiles)
 - Computation of the Endpoint

The Spearman-Kärber estimates (25th, 50th (median) and 75th percentiles) of dB thresholds for word recognition (Wilson et al., 1973) at each visit for treated ears will be computed as

$$dB = i + (p_c * d) - (d * w)/c$$

where "p_c" is the percentile of interest, "i" is the initial dB presentation level (fixed at 24), "d" is the attenuation dB step size (fixed at 4), "c" is the number of words per decrement (fixed at 10), and "w" is the frequency of words recognized overall at each visit. Missing data will not be imputed.

• Analysis of the Endpoint

Spearman-Kärber estimates (25th, 50th (median) and 75th percentiles) will be summarized descriptively for treated ears by visit and treatment group for subjects in the FAS.

For each post-baseline visit, scatter plots of the median Spearman-Kärber estimates at baseline versus the post-baseline visit will be produced for treated ears by treatment group for subjects in the FAS.

Version Date: 2023-01-19

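### The SAP's 25th and 75th percentile Words-in-Noise thresholds are always the median minus and plus 1 dB, so they add nothing to it and are not the 25% and 75% recognition points

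*SAP*

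**What the plan says.** SAP section 7.4.4 defines the 25th, 50th (median) and 75th percentile thresholds for treated ears by a single expression, dB = i + (`p_c` × d) − (d × *w*)/c. The starting level i is fixed at 24 dB, the step d at 4 dB and the words per step c at 10. The term `p_c` "is the percentile of interest", with no scale given, and *w* "is the frequency of words recognized overall at each visit".

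The planned output is that "Spearman-Kärber estimates (25th, 50th (median) and 75th percentiles) will be summarized descriptively for treated ears by visit and treatment group". Table 7-2 repeats the three percentiles. The scatter plots in 7.4.4, the change from baseline and MMRM in 7.4.5 and the ≥3 dB responder endpoint in 7.4.6 use the median only.

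SAP section 7.4 describes the test as 70 words per ear over seven signal-to-noise levels from 24 down to 0 dB, and section 7.4.1 uses 10 words as the denominator at each level. Section 7.4.1 also says that "the number of words classified as correctly recognized at each signal-to-noise ratio will be recorded", by visit and ear. Those per-level counts do not enter the 7.4.4 formula.

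**The concern.** A 25% or 75% recognition threshold is the signal-to-noise ratio at which a listener gets a quarter, or three quarters, of the words right. How far those points lie from the 50% point depends on the slope of the listener's recognition curve. A total word count fixes roughly where the curve sits but says nothing about its slope. A formula that uses only the total therefore cannot produce the two outer points.

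If the SAP is followed as written, the table will show three thresholds that look like three descriptions of the curve but are one measurement shown three times, with a constant added. A reader could take the agreement of the three rows as corroboration, or read the fixed gap between them as evidence that all curves are steep or that treatment leaves the slope unchanged. The table can show neither.

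**Working it through.** **Inputs.** All from SAP 7.4.4 except where noted: i = 24, d = 4, c = 10; *w* from 0 to 70 (70 words per ear, SAP 7.4). Assumption: `p_c` = 0.25, 0.50, 0.75. The SAP states no figure for these thresholds that could be reproduced.

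**Step 1: scale of `p_c`.** Entering 25, 50 and 75 at *w* = 35 gives 24 + 100 − 14 = 110, 24 + 200 − 14 = 210 and 24 + 300 − 14 = 310 dB, which is not plausible for a test run from 0 to 24 dB. Fractions are the only workable reading. The gaps are constant either way, because *w* cancels.

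**Step 2: substitute.**

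- 25th: 24 + 0.25 × 4 − 0.4*w* = 25 − 0.4*w*
- 50th: 24 + 0.50 × 4 − 0.4*w* = 26 − 0.4*w*
- 75th: 24 + 0.75 × 4 − 0.4*w* = 27 − 0.4*w*

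The difference between neighbouring percentiles is d × 0.25 = 1 dB.

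| *w* | 25th | 50th | 75th |
|---|---|---|---|
| 0 | 25 | 26 | 27 |
| 20 | 17 | 18 | 19 |
| 35 | 11 | 12 | 13 |
| 50 | 5 | 6 | 7 |
| 70 | −3 | −2 | −1 |

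Evaluating every *w* from 0 to 70 in half-word steps (half words can arise because the efficacy baseline averages two visits) gave offsets of −1 and +1 dB without exception. In the planned table the SDs of the three rows will be identical, and the means, medians, minima and maxima will differ by exactly 1 dB from row to row.

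**Step 3: are these the 25% and 75% points?** Take three illustrative profiles, assumed and not from the documents, each with *w* = 35. Words correct are listed from 24 dB down to 0 dB. The percentage points come from linear interpolation of the per-level proportions.

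| Profile | Words correct per level | Interpolated 25/50/75 (dB) | SAP formula 25/50/75 (dB) |
|---|---|---|---|
| Steep | 10, 10, 10, 5, 0, 0, 0 | 10 / 12 / 14 | 11 / 12 / 13 |
| Middle | 10, 9, 7, 5, 3, 1, 0 | 7 / 12 / 17 | 11 / 12 / 13 |
| Shallow | 8, 7, 6, 5, 4, 3, 2 | 2 / 12 / 22 | 11 / 12 / 13 |

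The interpolated 25-to-75 spread runs from 4 to 20 dB; the formula always gives 2 dB. With levels 4 dB apart and a monotone profile, interpolation gives 2 dB only when recognition falls from 10/10 to 0/10 between two adjacent levels (0.5 × 4 = 2).

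**Step 4: is the median sound?** At `p_c` = 0.50 the term `p_c` × d is the 2 dB half-step. Building the Spearman-Kärber mean from the per-level proportions, with 100% taken at 28 dB and 0% at −4 dB, gives 12.0 dB for all three profiles, the same as 26 − 0.4 × 35 = 12. The median formula is the ordinary estimate. Other values of `p_c` only move its constant.

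**The case against.** The strongest reply is that almost nothing depends on the two outer values. They appear in one descriptive summary. The fixed testing sequence in SAP 7.1.4 contains no Spearman-Kärber quantity, and the key secondary Words-in-Noise endpoint is the change in percentage of words recognized overall. No test, confidence interval or p-value changes. Sections 7.4.1 and 7.4.2 also already summarize recognition at each of the seven levels, so performance along the curve can be seen elsewhere. All of this stands: it limits the size of the point without making the formula right.

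Four stronger readings are tempting, and the documents do not support them:

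- A reader might infer that the outer values are empty. They still reflect *w*; they add nothing beyond the median.
- A reader might infer that the SAP's thresholds are wrong in general. The median is not.
- A reader might expect repeated changes from baseline and treatment comparisons for the 25th and 75th. The SAP plans those for the median only.
- A reader might attach a typical error in dB to the outer points. For logistic curves with scales of 2, 3 and 4 dB, the true spread would be 2 × scale × ln 3 = 4.4, 6.6 and 8.8 dB, but no document supplies those scales. The only figure that comes from the SAP is the fixed 2 dB spread.

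The SAP attributes the method to a 1973 publication that is not available here. Whether that source was applied correctly cannot be judged, and the point rests on the printed formula alone.

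**Conclusion.** The point holds as a specification error of small consequence. As written, section 7.4.4 yields two of three planned estimates that are the median shifted by exactly 1 dB and that do not measure what their labels say. This follows from the SAP's own constants, given one assumption: that `p_c` is a fraction. The profiles in the check are illustrations of how far the labels can mislead, not estimates for this trial's population.

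The effect is limited to the descriptive summary in 7.4.4. The median, its MMRM, the ≥3 dB responder analysis, and the primary and key secondary endpoints are not affected by this issue.

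**What to change.** Delete the 25th and 75th percentile estimates from SAP section 7.4.4 (heading, computation and summary) and from the matching row of Table 7-2, and report the median only. State that `p_c` = 0.50. The cost is a small text edit and fewer table rows. Little is lost, because the per-level percentages are already summarized.

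If the sponsor wants the 25% and 75% points, derive them per ear from the recorded counts (10 words at each of seven levels), by interpolation or a fitted curve. The SAP should then name the method and give a rule for ears whose 25% or 75% point falls outside 0 to 24 dB or whose fit fails. For example, an assumed logistic curve with mid-point 22 dB and scale 3 dB has its 75% point at 22 + 3 × ln 3 = 25.3 dB, above the highest level tested. This option needs no new data, but it adds a short per-ear calculation, and the result will be missing for some ears near floor or ceiling.

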2.3. Randomization

Subjects will be randomized in a 1:1 ratio to one of two groups (FX-322 or placebo, respectively). The randomization will be stratified for Visit 2 (Day -15) Maryland CNC Word Recognition Score (above or equal to 28% words in quiet correct and below 28% words in quiet correct) and unilateral versus bilateral hearing loss. A single injection of FX-322 or placebo will be administered on Day 1 by intratympanic injection in the study ear.

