7.4.5. Change from baseline in median Spearman-Kärber estimates

• Computation of the Endpoint

Frequency Therapeutics

Protocol No. FX-322-208

Change from baseline to each post-baseline visit in median Spearman-Kärber estimates will be computed as dB post-baseline – dB at baseline. Missing data will not be imputed.

• Analysis of the Endpoint

The change from baseline in median Spearman-Kärber estimates will be summarized descriptively for treated ears by visit and treatment group for subjects in the FAS.

In treated ears only for subjects in the FAS, post-baseline treatment group comparisons through day 90 for the change from baseline in median Spearman-Kärber estimate will be analyzed using a MMRM model. The model will include fixed covariates of treatment group, visit, interaction between visit and treatment group, baseline median Spearman-Kärber estimate, interaction between baseline median Spearman-Kärber estimate and visit, and randomization stratification factors. If the model fails to converge, the randomization stratification factors will be dropped from the model. An unstructured covariance will be used to model the within-subject errors. Linear contrasts will be constructed to estimate the treatment effect on the mean change from baseline in median Spearsman-Kärber estimate by visit (e.g., estimated LS Mean differences by visit).

Line graphs (with standard error bars) will be created for the adjusted (least squares) mean change from baseline in median Spearman-Kärber estimates for treated ears by postbaseline visit and treatment group for subjects in the FAS. Post-baseline visit will be plotted on the x-axis and the adjusted (least squares) mean change from baseline in median Spearman-Kärber estimates for treated ears will be plotted on the y-axis. Each treatment group will be presented as a separate line in the plot.

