7.4.6. Improvement ≥3 dB shifts in median Spearman-Kärber estimates from baseline

• Computation of the Endpoint

Improvement \geq 3 dB shifts in median Spearman-Kärber estimates at each post-baseline visit for treated ears will be computed as 1 if the post-baseline Spearman-Kärber estimate – baseline Spearman-Kärber estimate is \geq 3 and as 0, otherwise where the baseline and postbaseline Spearman-Kärber estimates are not missing. Missing data will not be imputed.

• Analysis of the Endpoint

The incidence of improvement ≥3 dB shifts in median Spearman-Kärber estimates at each post-baseline visit for treated ears will be summarized using frequencies and percentages by visit and treatment group for subjects in the FAS.

Post-baseline treatment group comparisons will be performed using the GEE model described in Section 7.4.3 for subjects in the FAS.

Version Date: 2	2023-01-19
-----------------	------------

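### The Words-in-Noise median threshold is a rescaled total word count: it gives a 50% point to ears that never reach 50%, its MMRM repeats the key secondary test, and its responder rule has the wrong sign

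*SAP*

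**What the plan says.** SAP 7.4 describes the WIN test as 70 words per ear, 10 at each of seven signal-to-noise ratios from 24 down to 0 dB. The count at each ratio is recorded by ear.

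SAP 7.4.4 gives one formula for the 25th, 50th and 75th percentile thresholds: dB = i + p_c × d - (d × w)/c. The constants i, d and c are fixed, and w "is the frequency of words recognized overall at each visit". The counts at the separate ratios do not enter. No rule is given for an ear that does not reach the percentile in question.

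Three inferential analyses bear on this:

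- SAP 7.4.2, the key secondary, fits an "MMRM model for change from baseline in percentage of recognized words overall".
- SAP 7.4.5 plans "post-baseline treatment group comparisons through day 90 for the change from baseline in median" threshold, also by MMRM.
- SAP 7.4.6 defines a responder as post-baseline minus baseline threshold of at least 3. It then states: "Post-baseline treatment group comparisons will be performed using the GEE model" of 7.4.3.

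SAP 7.1.4 puts only the 7.4.2 analysis of WIN in the fixed testing sequence. SAP 2.3 stratifies randomization on the Visit 2 Maryland CNC score in quiet: "above or equal to 28% words in quiet correct and below 28% words in quiet correct".

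**The concern.** A 50% threshold should be the level at which the ear gets half the words right. A formula that sees only the total cannot tell an ear that crosses 50% from one that never does, and it returns a number for both. The trial plans for ears with poor word recognition, so non-crossing ears are plausible. The clinical study report would then show thresholds, and treatment effects on them, for ears with no such threshold in the tested range.

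The other risk is one of reading. Table 7-2 lists the dB change and the 3 dB responder as efficacy endpoints with their own MMRM and GEE. If the dB result is the percentage result in other units, two matching p-values look like corroboration when there is only one finding. With its sign reversed, the responder table would report deterioration under the name of improvement.

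**Working it through.** **Inputs (all from the SAP).** i = 24 dB, d = 4 dB, c = 10 words (7.4.4). p_c = 0.25, 0.50 or 0.75, read as proportions; another reading moves only the constant and leaves change scores alone. Overall percentage = 100 × w/70 (7.4.1). Baseline = average of Lead-in and Day 1, with no rounding before analysis (Section 3). No WIN score unless all 70 words are assessed (7.4).

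**The plan's own figure.** 7.4.3 equates 10% with 7 words: 7/70 = 10.0%, and 7 levels × 10 words = 70. This reproduces.

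**Step 1: reduce the formula.**
- Median: 24 + 0.5 × 4 - 4w/10 = 26 - 0.4w
- 25th percentile: 25 - 0.4w
- 75th percentile: 27 - 0.4w

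The outer percentiles are fixed offsets of -1 and +1 dB from the median, not separately estimated quantities.

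**Step 2: ears that never reach 50%.** Such an ear has at most 4 of 10 correct at each level, so w runs from 0 to 28. The median then runs from 26 - 0 = 26.0 dB to 26 - 0.4 × 28 = 14.8 dB. At w = 5 it is 24.0 dB, the top tested level, so any w of 5 or more gives an in-range value.

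| Words correct, 24 down to 0 dB | w | Formula median | Reaches 50%? |
|---|---|---|---|
| 4,4,3,2,1,0,0 | 14 | 20.4 dB | no |
| 4,4,4,4,4,4,4 | 28 | 14.8 dB | no |
| 10,10,8,0,0,0,0 | 28 | 14.8 dB | yes |
| 8,7,6,5,4,3,2 | 35 | 12.0 dB | yes, at 12 dB |

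The second and third ears differ completely and receive the same threshold.

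**Step 3: change scores.** Change in dB = -0.4 × (change in words). One percentage point is 0.7 words, so change in dB = -0.4 × 0.7 = -0.28 × (change in percentage points), for every ear. Averaging the two baseline visits preserves this.

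**Step 4: the two MMRMs.** 7.4.2 and 7.4.5 share treatment, visit, their interaction, baseline, baseline by visit, stratification factors, unstructured covariance, FAS, treated ears, the period through Day 90 and the convergence fallback. Outcome and baseline covariate are linear rescalings, so each treatment contrast and its standard error are multiplied by -0.28 and 0.28 respectively, and |t| is unchanged.

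This was checked by fitting both models to three simulated trials of 62 per arm. The word-recognition rates and about 6% missing visits are assumptions that serve only to show the identity; p-values use the normal approximation. Day 90 contrasts:

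| Trial | Percentage points | dB | \|z\| in both | p in both |
|---|---|---|---|---|
| 1 | 2.0883 | -0.5847 | 1.7711 | 0.07655 |
| 2 | 2.3192 | -0.6494 | 2.0792 | 0.03760 |
| 3 | 0.7858 | -0.2200 | 0.5993 | 0.54900 |

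The ratio of estimates is -0.2800 each time.

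**Step 5: the 3 dB responder.** As written, post-baseline minus baseline ≥ 3 means -0.4 × (change in words) ≥ 3, so change in words ≤ -7.5: a loss. Taken literally, no ear can meet both this flag and the 7-word responder of 7.4.3. With the sign corrected, the rule is a gain of at least 3/0.4 = 7.5 words (10.7%), against 7 words (2.8 dB) in 7.4.3. With a two-visit average baseline, gains move in half-words, so the two flags differ only at a gain of exactly 7.0 words.

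**The case against.** The strongest defence is that little depends on these endpoints. Only the percentage MMRM carries alpha, and 7.4.5 and 7.4.6 support no confirmatory claim. The formula is printed in full with its source. The percentages at each ratio, including 24 dB, are summarized by arm and visit, so performance at the easiest level is not hidden. One score in two units is redundant rather than invalid. All of this stands, and it limits the importance of the point. It does not supply a rule for non-crossing ears or tell a reader that the two p-values are one.

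Four stronger readings are tempting and should be resisted:

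- **That the formula gives a true 50% point only for ears going from near 100% to near 0% across the range.** It does not need that. The 8,7,6,5,4,3,2 ear is truncated equally at both ends and its value is correct.
- **That ears in the stratum below 28% mostly lack a 50% point in noise.** The documents do not relate the two tests. The quiet score uses Maryland CNC words at 30 dB above the ear's own pure tone average, or at the most comfortable level. WIN uses NU-6 words at 80 dB SPL. Neither document says how many subjects fall below 28%.
- **That the duplicate test inflates type I error.** It does not, because it is outside the fixed sequence.
- **That the 3 dB responder, as the SAP stands, nearly duplicates the 10% responder.** That is so only after the sign is reversed.

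**Conclusion.** The point holds, with modest consequences. The median threshold is 26 - 0.4w for every ear, so an ear that never reaches 50% is still assigned a 50% threshold of 14.8 to 26.0 dB. The formula itself is a sensible summary for many ears; the fault lies in presenting it as a 50% point for all of them. How many ears are affected cannot be determined from the documents.

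The 7.4.5 MMRM gives the same |t| and p-value as the key secondary. This rests on the same records entering both models, which the scoring, baseline and rounding rules imply, and on both fits using the same convergence path. It adds no independent evidence. The 7.4.6 rule is reversed as written. No confirmatory conclusion changes; what is at risk is how the secondary WIN results are read.

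**What to change.** 1. Remove the 7.4.5 MMRM and the 7.4.6 GEE as separate tests. Report the 7.4.2 LS mean difference and confidence interval with the dB equivalent (multiply by -0.28, which swaps the interval ends), labelled as a rescaling.
2. If the 7.4.6 responder summary is kept, define improvement as baseline minus post-baseline of at least 3 dB.
3. In the descriptive threshold summaries, use the counts already recorded at each ratio to flag ears with fewer than 5 of 10 correct at every tested level as not reached (>24 dB). Do not present the formula value as their 50% threshold.

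The cost is SAP wording and fewer tables, with no new data. Some ears will have no reported threshold. With 10 words per level, the standard error at 50% is √(0.5 × 0.5/10), about 16 percentage points, so ears near the boundary may change flag between visits by chance. That is tolerable in a descriptive summary, and it is a reason not to build a new responder test on the flag. No ear need be excluded from the 7.4.2 analysis.
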